### **4.1. DESCRIPTION OF MEASURES TAKEN TO REDUCE AND AVOID BIAS**

Consecutive recruitment with provision of sampling frame data.

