## **5. STUDY FEASABILITY**

The clinical research associate (CRA) delegated by the sponsor will make two or three visits to the investigational center:

- An inclusion visit to confirm the investigator's adherence to the protocol and to define the procedures for extracting and transferring anonymized data from the electronic patient record management system. As this is a single-center study, this visit will take place before the protocol is submitted to the CNIL.
- A visit to extract and transfer anonymized data from patient files, and to call patients to obtain their two-year follow-up data. On this occasion, patients will be informed that they may object to the inclusion of their information in this study. During this visit, the sponsor's clinical research associate will check that the data are consistent with the contents of the patient files. He/she will confirm the completeness of the cohort, with consecutive placement of dual-mobility acetabular implants. An anonymized list of all THA during the recruitment period will be obtained and checked to establish the sampling frame. This visit will take place at the start of the study.
- An additional visit by the CRA, to obtain missing data and resolve discrepancies, will take place if necessary.

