### **10.2. DATA ANALYSIS – GENERAL INFORMATION: DESCRIPTIVE APPROACH**

- Descriptive statistics: preoperative, operative, postoperative
- Tabulation of adverse events
- Kaplan-Meier analysis of implant survival
- Comparison tests of preoperative versus 1-year and 2-year postoperative efficacy scores.

Tests will be performed with a two-side alpha risk of 5%. Confidence intervals will be at 95%.

Continuous variables will be tested using Student's t-test. Categorical variables will be tested using Chi-2 test.

No subgroup analysis is planned.

No interim analysis is justified given the strict retrospective nature of the study.

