### **10.5. SAMPLING FRAME**

The sampling frame, i.e. all patients operated by the same surgeon in the same institution, for total hip replacement, between the first and the last date of inclusion of patients in the SYMBOL CUP DMR HA or SYMBOL CUP DM CEM cohort, will be the subject of descriptive statistics.

Analysis will focus on age at date of operation, BMI, type of prosthesis, 1st intention or revision (See Questions relating to the sampling frame Annex 2).

Its characteristics will be compared to those of the cohort.

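### The sampling frame in 10.5 contains the cohort, so comparing the two shrinks any real selection difference by the cohort's share of the frame

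*Combined protocol and SAP*

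**What the plan says.** Section 10.5 defines the sampling frame as "all patients operated by the same surgeon in the same institution, for total hip replacement, between the first and the last date of inclusion" of the patients in the cohort. The source is consistent with that: under section 5 (repeated in 6.1), "An anonymized list of all THA during the recruitment period will be obtained and checked to establish the sampling frame". Neither place removes cohort patients from the frame.

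Section 10.5 states that the frame "will be the subject of descriptive statistics" and lists the variables: "Analysis will focus on age at date of operation, BMI, type of prosthesis, 1st intention or revision". It closes with the comparison: "Its characteristics will be compared to those of the cohort". It names no method for that comparison.

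The general rules in 10.2 set a two-sided 5% alpha and 95% confidence intervals, and state that "Continuous variables will be tested using Student's t-test", with Chi-2 for categorical variables. Section 10.4 repeats these and allows non-parametric alternatives.

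On bias, the whole of section 4.1 is: "Consecutive recruitment with provision of sampling frame data". Sections 5 and 6.1 add a check by the clinical research associate (CRA) that the consecutive cohort is complete.

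**The concern.** Every cohort operation meets the frame definition: same surgeon, same institution, and inside the date window by construction. The procedure also fits if the frame's total hip replacements include revisions, which the first-intention-or-revision variable implies. The cohort is therefore counted on both sides of the comparison, and the contrast is pulled towards similarity even if nobody computes a p-value.

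The CRA check shows whether all recipients of these cups were captured. It does not show whether those recipients differ from the surgeon's other patients. The frame comparison is the only planned analysis that does. Such differences are to be expected: section 2.1 says these fixations are chosen when bone damage is extensive, notably in revision surgery. Section 2.2 says the results will support CE-mark renewal and a reimbursement application, where readers need an undiluted account of who was treated.

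**Working it through.** The documents give no frame size, expected difference or power for this comparison, so there is no planned figure to reproduce. The effect of the overlap is derived below.

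**Inputs**
- From the plan: n = 20, the minimum cohort size (10.1); two-sided alpha 5% (10.2).
- Assumed: N = 200, 100 or 50; a true cohort-versus-others difference of 0.7 SD; a common SD s in both groups; normal approximation.

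**Step 1: attenuation (no test needed).** The frame mean is (n × cohort mean + (N − n) × others' mean)/N. Therefore

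cohort mean − frame mean = (1 − n/N) × (cohort mean − others' mean).

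The same holds for proportions. The loss is n/N:
- N = 200: 20/200 = 10%
- N = 100: 20/100 = 20%
- N = 50: 20/50 = 40%

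As an illustration, assume revision shares of 60% in the cohort and 10% in the others. The 50-point gap appears as 45 points at N = 200 (50 × 0.9), 40 at N = 100 (50 × 0.8) and 30 at N = 50 (50 × 0.6).

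**Step 2: if an independent-samples test were applied.** The test would assume SE = s√(1/n + 1/N). Because the cohort is part of the frame, the true SE is s√(1/n − 1/N). The test is then too conservative, on top of the attenuation.

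At N = 100, with s = 1:
- Assumed SE = √(0.05 + 0.01) = 0.245; true SE = √(0.05 − 0.01) = 0.200.
- Type I error: 1.96 × 0.245/0.200 = 2.40, and 2 × (1 − Φ(2.40)) = 1.6%.
- Power with overlap: the expected difference is 0.7 × 0.8 = 0.56 and the rejection threshold is 1.96 × 0.245 = 0.480. Φ((0.56 − 0.480)/0.200) = Φ(0.40) = 66%.
- Power against the 80 other patients: SE = √(1/20 + 1/80) = 0.250. Φ(0.7/0.250 − 1.96) = Φ(0.84) = 80%.

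The same formulas for the other sizes:

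| Assumed N | Attenuation | Actual type I error (nominal 5%) | Power, cohort vs frame | Power, cohort vs others |
|---|---|---|---|---|
| 200 | 10% | 3.0% | 79% | 84% |
| 100 | 20% | 1.6% | 66% | 80% |
| 50 | 40% | 0.3% | 28% | 68% |

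A simulation of 20,000 t-tests per setting agrees where it was run: type I error 2.8% at N = 200 and 1.5% at N = 100 with overlapping groups, against 5.0% and 4.9% with separate groups.

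**The case against.** **The analysis is called descriptive and no test is named.** This stands. The comparison tests itemised in 10.2 concern preoperative versus postoperative efficacy scores. A reader might infer that the plan prescribes an invalid test of frame against cohort. The documents do not say so; that reading only borrows the general rules of 10.2 and 10.4. Step 2 is conditional on it, but Step 1 is not.

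**It is not the only safeguard against bias.** This also stands. Section 4.1 lists consecutive recruitment first, and the CRA completeness check follows in sections 5 and 6.1. The narrower statement holds: it is the only planned statistical check on who was selected.

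**Differences are attenuated, not hidden.** This stands in part. If n, N and both summaries were reported on complete data, the others' mean or proportion could be recovered as (N × frame − n × cohort)/(N − n). The plan does not commit to reporting those quantities, and a p-value from overlapping groups would still be wrong. A large revision imbalance would stay visible, as the illustration shows.

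**The larger losses need a small frame.** This is fair. The EC declaration of conformity dates from April 2014, and two years of follow-up by 1 March 2018 implies surgery by about March 2016, a window of at most about 23 months. Over that full window N = 50 would be about 2 operations a month (50/23), for a surgeon whose activity Annex 5 describes as substantial. The actual window could be shorter, so a small frame cannot be excluded.

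**Simply removing the cohort is imprecise.** The remainder could include recipients of the study cups who were not included, for example after refusal or because of guardianship (7.2). This is right, and the fix allows for it.

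The sampling-frame questions that 10.5 places in Annex 2 are not in the text available for review. Nothing here treats them as missing.

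**Conclusion.** The point holds as a defect in the comparison rule of 10.5. As defined, the frame includes the cohort, and the stated comparison understates any real cohort-versus-others difference by n/N. With n = 20 that is 10%, 20% or 40% at assumed frame sizes of 200, 100 or 50. The loss is minor if the cohort is 5–10% of the frame and serious only if it is a large share. The documents do not allow the share to be fixed.

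The type I error and power figures apply only if the t-test and Chi-2 rules are extended to this comparison, and the power figures also rest on an assumed 0.7 SD difference.

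A reader might go further and infer that the implant survival result is biased. The documents do not support that. The study is non-comparative, its main analysis is Kaplan-Meier survival in the cohort alone, and the frame comparison enters no survival, dislocation or Harris Hip Score estimate. What is affected is the reader's judgement of how far the results generalise.

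**What to change.** Replace the last sentence of 10.5 with:

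> Characteristics of the cohort will be compared with those of the other frame patients (frame minus cohort), reported as differences with 95% confidence intervals; the whole frame will be described separately, and any recipients of the study cups not included in the cohort will be counted separately.

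Differences with intervals suit the descriptive aim and need no significance test. If one is applied under 10.2 or 10.4, the two groups no longer share patients.

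The cost is one sentence in the plan and one filter on the frame file. No new data are needed, and the primary analysis does not change. The cohort may look slightly less like the surgeon's other patients than it would under the current wording.

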## 2. STUDY RATIONALE / SCIENTIFIC JUSTIFICATION

### 2.1. CURRENT KNOWLEDGE OF THE PATHOLOGY

Hip replacement is the last therapeutic resort for symptomatic coxopathies, the incidence of which is estimated at over 85,000 patients per year, if hip replacement is considered as an indicator of this

pathology, according to data from the Programme de Médicalisation des Systèmes d'Information (PMSI).

In the report of 2014, the Haute Autorité de Santéi, recommends the use of dual-mobility acetabular implants:

- In first-line arthroplasties in patients with a very high risk of dislocation (severe neurological impairment, neuropsychiatric disorders, addiction, and major neuromuscular failures),
- And revision arthroplasties in case of iterative dislocation and in patients at high risk of dislocation,
- Depending on the clinical situation, press-fit fixation is the preferred method of fixation for the metal-back dual mobility acetabular cups, when the bone bed is of good quality.

In current practice, dual-mobility acetabular implants with cemented fixation in a cross shell, or with cortical screws and peg, are chosen when damage to the bed bone is extensive and does not allow direct press-fit implantation. This is particularly the case in revision surgery.

SYMBOL CUP DMR HA acetabular implants comprise metal-back cup with cortical screw fixation and peg fixation and the same DUAL MOBILITY PE LINER dual-mobility polyethylene insert as in all acetabular implants in the SYMBOL CUP DM range (Table 1, Figure 1).

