# **7. ELIGIBILITY CRITERIA**

## **7.1. INCLUSION CRITERIA**

Any patient operated by [name] who has undergone hip replacement surgery with SYMBOL CUP DMR HA or SYMBOL CUP CEM acetabular implant and having reach 2-year follow-up on March 01, 2018.

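### The sampling-frame comparison in section 10.5 mixes the indication for the study cups with selection into the cohort, so it cannot show whether the series is unselected

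*Combined protocol and SAP*

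**What the plan says.** Section 4.1 (measures to reduce and avoid bias) has a single entry: "Consecutive recruitment with provision of sampling frame data".

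Section 10.5 defines the frame as "all patients operated by the same surgeon in the same institution, for total hip replacement", between the first and last inclusion dates of the cohort. It continues: "Analysis will focus on age at date of operation, BMI, type of prosthesis, 1st intention or revision". Then: "Its characteristics will be compared to those of the cohort". It names no test and does not restrict the comparison to recipients of the study cups. It refers to frame questions in Annex 2, which are not in the text available to me.

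Section 7.1 defines the cohort as patients with "hip replacement surgery with SYMBOL CUP DMR HA or SYMBOL CUP CEM acetabular implant and having reach 2-year follow-up on March 01, 2018".

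Section 2.1 says that dual-mobility cups cemented into a cross shell, or fixed with cortical screws and peg, "are chosen when damage to the bed bone is extensive and does not allow direct press-fit implantation", and adds: "This is particularly the case in revision surgery".

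Sections 5 and 6.1 have the sponsor's clinical research associate (CRA) confirm that the cohort is complete and consecutive, and obtain and check a list of all hip replacements in the period. Annex 2 records, for each cohort patient, the order number of the operation with that type of implant.

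**The concern.** The selection question is whether the patients analysed represent everyone who received a study cup in the window. That needs included recipients set against recipients who were not included. Section 10.5 instead sets the cohort against a population defined without regard to the cup. If the cups are used for particular indications, the two groups differ however complete recruitment was. If some recipients were left out, the difference may grow, shrink or disappear, depending on who they were.

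Section 2.2 says the results will support CE-mark renewal and a reimbursement application. Section 10.1 sets a minimum of 20 patients. At that size each omitted failure matters: 20 of 20 is 100%, 20 of 21 is 95%, and 20 of 24 is 83%, or about 4 to 5 percentage points of crude survival per failure. A reader will want to know whether recipients are missing, and may take the sampling-frame table as the answer.

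**Working it through.** **Plan's own figure.** The only stated number that bears on this is the minimum of 20, justified by other manufacturers' studies. Without an effect size or precision target there is nothing to reproduce. The point is structural, and the numbers below illustrate it.

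**Inputs from the documents.** Cohort of 20 (10.1); two-sided 5% and chi-2 for categorical variables (10.2). Section 10.5 itself names no test, so applying chi-2 there is an assumption.

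**Assumed inputs.** Frame size, and revision shares among recipients and among other patients.

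**Step 1: complete recruitment.** Cohort = every recipient, n = 20. There are 200 other hip replacements with a 10% revision share. Chi-2 without continuity correction is applied to first-line/revision status.

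| Revision share in recipients | Chance of p<0.05, cohort vs others |
|---|---|
| 10% (equal) | about 4% |
| 30% | 69% |
| 40% | 91% |
| 50% | 99% |
| 70% | about 100% |

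With the cohort counted inside the frame, as 10.5 is worded, the chance is 61% at a 30% share, 98% at 50%, and about 2% at equal shares. For total frames of 100 to 400 it runs from 41% to 66% at 30%, and from 92% to 99% at 50%. In every row, nobody eligible was left out.

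**Step 2: selective recruitment in a worked example.** Frame 200: 30 recipients with 15 revisions, and 170 others with 17, so 32 of 200 in all. For a 2×2 table, chi-2 = N(ad − bc)² / (product of the four margins).

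- All recipients included, 15/30 vs 32/200: 230 × (15×168 − 15×32)² / (47×183×30×200) = 18.5, p<0.0001.
- Ten revision recipients left out, 5/20 vs 32/200: 220 × (5×168 − 15×32)² / (37×183×20×200) = 1.05, p = 0.30.
- Included vs not-included recipients, 5/20 vs 10/10: Fisher p = 0.0002.

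The planned comparison signals a difference when recruitment is complete and none when it is selective. The comparison within recipients shows the selection.

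**Step 3: how far omission moves the result.** Take 24 recipients, 4 of them failures with a 70% revision share, and 200 others at 10%.

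- Overall recipient share 30%: the remaining 20 have (0.30×24 − 0.70×4)/20 = 22%. Omitting the 4 failures cuts the rejection rate from 75% to 39%. With the cohort inside the frame it falls from 66% to 25%.
- Overall recipient share 50%: the remaining 20 have (0.50×24 − 0.70×4)/20 = 46%. The rate goes only from 99% to 97%, because it is already near its ceiling.

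The effect of omission therefore depends on a case mix that the documents do not give.

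**Step 4: type of prosthesis.** If it is coded as study cup or not, 20/20 vs 20/220 gives 240 × (20×200 − 0×20)² / (40×200×20×220) = 109.1, p<1e-24, by construction. The frame's coding is not in the available text, so this holds only under that coding.

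**The case against.** The strongest objection concerns purpose. Section 10.5 calls the frame a subject for descriptive statistics and nowhere says the comparison tests selection. Showing how recipients differ from the surgeon's other patients is legitimate context. This stands in part, and the comparison should be kept for that use. But section 4.1 places frame data under measures against bias and lists nothing else, so readers will use it that way.

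Selection is also addressed elsewhere. The CRA confirms completeness on site, and the order number could reveal a gap in the series. This stands too, and a reader who inferred that selection goes unchecked would be wrong. What is missing is a reported result: section 10 plans no count or comparison of included and non-included recipients.

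Three stronger readings are tempting and not supported:

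- That the comparison gives the same answer whether or not recipients were left out. Step 3 contradicts this. It responds to omission, but not in a way that can be separated from indication.
- That the protocol itself says the cohort and frame must differ. Section 2.1 fits DMR HA well. It fits DM CEM less surely: section 2.1 describes that cup as cemented to the surrounding bone, and section 2.2 places it under a standard-cup code. The mix of the two cups is not stated. Differences in age, BMI and revision status are expected, not certain.
- That recipients were in fact omitted. Nothing in the documents shows this.

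**Conclusion.** The concern holds as a matter of interpretation. The reference population in 10.5 is wider than the eligible population, so a difference mixes indication with selection, and a lack of difference does not exclude selection. The comparison can neither support nor refute a claim that the survival estimate comes from an unselected series. Correcting the test, the overlap of cohort and frame, or the dates would not change this.

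The size cannot be established from the documents. The rejection rates and p-values rest on assumed frame sizes and revision shares and on a chi-2 test that 10.5 does not name. The conclusion needs only that the cups are used selectively, which section 2.1 supports most clearly for DMR HA. The primary Kaplan-Meier analysis is unaffected. What changes is what the report can say about how representative the series is.

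**What to change.** In section 10.5:

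1. From the all-hip-replacement list already obtained, report how many patients received SYMBOL CUP DMR HA or DM CEM in the window, how many were included, and how many were not, by reason (refusal, other exclusion). Report any gaps in the implant order number.
2. Describe age, BMI and first-line/revision status for included and non-included recipients, without p-values. For patients who objected under sections 7.2 and 12.2, use only data that may still be used; where none may be, report the count alone.
3. Keep the comparison with the other hip replacements as a description of who receives these cups. Do not test type of prosthesis in it, and state that it is not evidence about selection.

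The cost is a few sentences and one small table. The list and its prosthesis-type field are already planned. The non-included group will be small or empty, and age, BMI and revision status would not directly reveal omitted failures, so the count is the main output.

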### **10.6. METHOD FOR TAKING INTO ACCOUNT MISSING, UNUSED OR INVALID DATA**

As the statistical analysis is descriptive, it will be carried out « *per protocol* » and missing data will not be substituted by values derived from hypotheses.

Visibly aberrant data that the investigator cannot obtain through the usual telephone follow-up will be excluded from the analysis.

Adverse event or follow-up dates for which the day is missing will be substituted by the mid-month date.

### **10.7. PERSON RESPONSIBLE FOR THE ANALYSIS**

[name]

Biostatistician

MEDEXTENS SARL

[name]

[contact]

Mail: [contact]

Software used:

Data was analyzed in STATA 14.2 MP - Parallel Edition, 64-bit

StataCorp

[name]

[name]

2-core Stata perpetual license:

Serial number: 501406000407

Licence de Medextens SARL

## **11. ACCESS RIGHTS TO SOURCE DATA AND DOCUMENTS**

### **11.1. DATA ACCESS**

The sponsor is responsible for obtaining the agreement of all parties involved in the study to guarantee direct access to all research sites, source data, source documents and reports for the purposes of quality control and audit by the sponsor.

Investigators will make available documents and individual data strictly necessary for the monitoring, quality control and auditing of biomedical research to persons with access to these documents in accordance with the legislative and regulatory provisions in force (articles L.1121-3 and R.5121-13 of the French Public Health Code).

### **11.2. SOURCE DATA**

Any original document or object that can be used to prove the existence or accuracy of a data item or fact recorded during the course of the research is defined as a source document.

The source data is exclusively the patient file located in the clinic where the patients included in the study were operated on, and under the responsibility of the surgeon.

The sponsor's CRA will be not able to obtain a copy of source data but may ask to check them to ensure the accuracy of the final database.

### **11.3. DATA PRIVACY**

In accordance with current legislation (articles L.1121-3 and R.5121-13 of the French Public Health Code), persons with direct access to source data must take all necessary precautions to ensure the confidentiality of information relating to investigational medicinal products, research, the persons

---

involved, and in particular their identity, as well as the results obtained. These persons, like the investigators themselves, are bound by professional confidentiality.

During biomedical research or at its termination, the data collected on the persons involved and transmitted to the sponsor by the doctors (or any other specialist) will be rendered anonymous. Under no circumstances may the names or addresses of the persons concerned should appear in clear text.

Patients will be coded by serial number. No initials will be recorded. Identification by the surgeon will be by month/year of birth, gender and date of surgery.

Source data form an integral part of the patient file.

The spreadsheet with extracted data sent to the sponsor will be kept for 30 years after the medical device is withdrawn from the market.

The copy held by the statistician with the statistician scripts and data tables will be deleted by him from his company's computer as soon as the study report has been signed and submitted.

